During the screening period, all patients will undergo the informed consent process and standard screening procedures. Laboratory assessments used to determine eligibility may be repeated once during the screening period. Patients who do not meet eligibility criteria during the initial screening may rescreen only once; only the assessments that did not meet eligibility criteria initially are required to be repeated, if rescreening occurs within the screening period. Patients who are rescreened after the screening window ends must re-consent for study participation and repeat all screening procedures.

After confirmation of eligibility at visit 2, all patients will receive an IV bolus of 60 IU of heparin per kg of body weight and a blood sample will be collected to assess baseline level of LPL enzyme activity.

Assignment into 1 of the 3 cohorts and enrollment into the study will occur at visit 3 for patients meeting eligibility.

If enrollment into a specific cohort has reached the maximum number allowed, the patient will not be eligible for enrollment.

Baseline/Single-Blind Placebo Run-in Period (Day -28 to Day -1)

Principal investigators, study site personnel, and the Regeneron study team will be unblinded to treatment, but study patients will not. On day -28, all patients will receive a single IV placebo infusion. Patients will be closely monitored for a minimum of 120 minutes after IV administration of placebo on day -28.

Double-Blind Treatment Period (Day 1 to Day 85)

Principal investigators, study site personnel, study patients and the Regeneron study team will all be blinded to treatment during the double-blind treatment period.

Patients will be randomized 2:1 (evinacumab:placebo) to receive either evinacumab administered IV at a dose of 15 mg/kg or matching placebo every 4 weeks (± 4 days) on days 1, 29, and 57. Patients will be closely monitored for a minimum of 120 minutes after IV administration of evinacumab or matching placebo on days 1, 29, and 57.

Stable doses of other triglyceride-lowering therapies, such as fibrates, statins, omega-3s, and niacin are allowed during the study. Patients may not take Glybera[®], mipomersen, or lomitapide during the study.

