Efficacy and safety procedures and completion of the pancreatitis daily symptom questionnaire and symptom/dietary impact questionnaire will be performed as outlined in the schedule of events. Imaging correlates of pancreatic health will be assessed by ¹⁸F-FDG PET, by DW-MRI, and by T2-MRI.

Serum samples for the determination of total evinacumab, total ANGPTL3, and anti-drug (anti-evinacumab) antibodies (ADA) will be collected.

Serum and plasma samples will be collected for analysis of additional biomarkers, including amylase and lipase.

Single-Blind Treatment Period (Day 86 to Day 169)

All patients who complete the double-blind treatment period will receive evinacumab administered IV at a dose of 15 mg/kg every 4 weeks (± 4 days) on days 85, 113, and 141.

Stable doses of other triglyceride-lowering therapies, such as fibrates, statins, omega-3s, and niacin are allowed during the study. Glybera[®], mipomersen, or lomitapide are prohibited during the study.

Efficacy and safety procedures and completion of the pancreatitis daily symptom questionnaire and symptom/dietary impact questionnaire will be performed as outlined in the schedule of events. Patients should fast for a minimum of 8 hours prior to any blood draws. Imaging correlates of pancreatic health will be assessed by DW-MRI.

Serum samples for the determination of total evinacumab, total ANGPTL3, and anti-drug (anti-evinacumab) antibodies (ADA) will be collected.

Serum and plasma samples will be collected for analysis of additional biomarkers, including amylase and lipase.

Off-Drug Treatment Follow-up Period (Day 170 to Day 309 [End-of-Study])

Efficacy and safety procedures will be performed as outlined in the Schedule of Events.

Throughout the Study

Patients will be reminded at visits and during phone calls to adhere to a highly effective birth control method. Pregnancy status of female patients of childbearing potential and of female partners (of child-bearing potential) of male patients will be monitored throughout the study and for 24 weeks post the last dose of study drug.

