5.8. Analysis of Safety Data

The summary of safety results will be presented separately for the DBTP and SBTP, unless otherwise noted. Safety summaries for the DBTP will be presented by treatment groups (evinacumab, placebo), as well as by treatment group within each cohort containing patients from the double-blind safety analysis set. Safety summaries for the SBTP will be presented by all patients and by treatment group in DBTP (i.e., evinacumab, placebo), for patients in the single-blind safety analysis set. No formal inferential testing will be performed for either period. Summaries will be descriptive in nature.

General common rules

All safety analyses will be performed, unless otherwise specified, using the following common rules:

- Safety data in patients who do not belong to the safety analysis set (i.e., exposed but not randomized) will be listed separately.
- PCSV values are defined as abnormal values considered medically important by the Sponsor according to predefined criteria/thresholds based on literature review and defined by the Sponsor for clinical laboratory tests and vital signs (PCSV version dated January 2009 [[Appendix 10.3](#)]). Considering that the threshold defined in the PCSV list for monocytes and basophils can be below the ULN, the following PCSV criterion will be used for the PCSV analysis of monocytes and basophils:
 - PCSV criterion for monocytes: >0.7 Giga/L or $>\text{ULN}$ (if $\text{ULN} \geq 0.7$ Giga/L).
 - PCSV criterion for basophils: >0.1 Giga/L or $>\text{ULN}$ (if $\text{ULN} \geq 0.1$ Giga/L).
- PCSV criteria will determine which patients had at least 1 PCSV during the respective TEAE periods, taking into account all evaluations including unscheduled or repeated evaluations.
- For summary tables, only protocol scheduled measurements (as defined by e-CRF visit label) will be included. Patient listings will include all measurements, scheduled and unscheduled.
- The treatment-emergent PCSV denominator by treatment group for a given parameter will be based on the number of patients assessed for that given parameter at least once during the respective TEAE periods.
- For quantitative safety parameters including central laboratory measurements and vital sign scores, descriptive statistics will be used to summarize observed values and change from baseline values by visit.

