5.8.5. Clinical Laboratory Measurements

For respective treatment period (DBTP and SBTP), clinical laboratory parameter actual values (quantitative) and change from baseline values will be descriptively summarized at baseline and each post-baseline visit (collected up to the day of last dose of study treatment +28 days) by at least patient number, mean, median, Q1, Q3, SD, minimum and maximum. Clinical laboratory parameters mean changes from baseline, with the corresponding SE, can be plotted at each visit in the case results warrant further investigation. These parameters will be presented by the biological functions defined in Section 4.8.2. For glucose, only fasting samples will be included in the summaries.

Individual patient laboratory parameter measurements will be additionally evaluated by PCSV criteria (See [Appendix 10.3](#)), specifically identifying patients with at least one post-baseline

measurement that meets the PCSV criteria within the respective TEAE periods. These laboratory parameters will be presented by the biological functions defined in Section 4.8.2. The incidence of PCSVs at any time during the respective TEAE periods will be summarized regardless of the baseline level, and again according to the following baseline categories:

- Normal (according to PCSV criterion/criteria)/missing
- Abnormal according to PCSV criterion or criteria

Patient listings of laboratory measurements that meet PCSV criteria will be provided for the report appendix. For those laboratory parameters that don't have an associated PCSV criteria, similar summary tables can be provided based on measurements outside the central laboratory normal ranges, if applicable.

Drug-induced liver injury

For respective treatment period (DBTP and SBTP), an evaluation of drug-induced serious hepatotoxicity (eDISH) with the graph of distribution of peak values of ALT versus peak values of total bilirubin will also be presented using post-baseline values during respective TEAE periods. Note that the ALT and total bilirubin values are presented on a logarithmic scale. The graph will be divided into 4 quadrants with a vertical line corresponding to 3 x ULN for ALT and a horizontal line corresponding to 2 x ULN for total bilirubin.

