5.8.6. Analysis of Vital Signs

For respective treatment period (DBTP and SBTP), the vital sign actual values and change from baseline values obtained while sitting will be descriptively summarized at baseline and each post-baseline visit (collected up to the day of last dose of study treatment +28 days) by at least patient number, mean, median, Q1, Q3, SD, minimum and maximum. Vital sign mean changes from baseline, with the corresponding SE, can be plotted at each visit in the case results warrant further investigation.

Individual patient vital sign measurements (regardless of sitting position) will be additionally evaluated by PCSV criteria, specifically identifying patients with at least one post-baseline measurement that meets the PCSV criteria within the TEAE period. The incidence of PCSVs at any time during the respective TEAE periods will be summarized regardless of the baseline level, and again according to the following baseline categories:

- Normal (according to PCSV criterion/criteria)/missing
- Abnormal according to PCSV criterion or criteria

Patient listings of vital sign measurements that meet PCSV criteria will be provided for the report appendix.

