10.4.1. Footnotes for the Schedule of Events Table

1. Patients who are permanently withdrawn from study drug before entering the double-blind treatment period (day 1, week 0) will be contacted to assess any AEs.
2. Patients who are permanently withdrawn from the study drug during double-blind period will be asked to return to the clinic for an early termination visit consisting of week 12 study assessments. After the early termination visit, patients will enter the off-drug treatment follow-up period.
3. Patients who are permanently withdrawn from study drug during the single-blind treatment period will be asked to return to the clinic for an early termination visit consisting of week 24 study assessments. After the early termination visit, patients will enter the off-drug treatment follow-up period.
4. Visit 1b must occur at least 4 days after visit 1.
5. Patients will undergo end of double-blind treatment period assessments at the week 12 visit, which is the first visit of administration of single-blind evinacumab.
6. Medical history should include detailed cardiovascular and pancreatitis history.
7. The patient should be fasting for at least 8 hours prior to the post-heparin procedure for measurement of LPL activity. The patient should not consume any alcohol 48 hours prior to the post-heparin plasma blood draw. Heparin (60 U/kg body weight) should be administered IV by bolus injection. Venous blood should be collected 10 minutes after the bolus injection. Prior to discharge from the clinic, patients should then be observed for 1 hour post-heparin administration for any AEs.
8. Following the screening period and confirmation of eligibility, patients will receive an IV bolus of 60 IU of heparin per kg of body weight at visit 2.
9. At dosing visits, all assessments (including urine or serum pregnancy tests for WOCBP) should be performed and all blood samples should be collected before the dose of study drug is administered.
10. Vital signs should also be measured and AEs monitored pre-dose, at the end of study drug infusion, between 30 to 60 minutes post dose, and at approximately 120 minutes post dose. Patients will be closely monitored for a minimum of 120 minutes after IV administration of study drug.
11. Patients should fast for a minimum of 8 hours prior to all blood draws. For patients with diabetes, investigators may hold a patient's morning diabetes medications until labs are drawn and the patient has eaten.

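### The 28-day limit on by-visit laboratory and vital-sign summaries falls on the nominal week 24 visit day (and week 12, if last dose is read per period), so on-window end-of-period values can drop out of the tables

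*SAP*

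**What the plan says.** SAP 5.8.5 summarises laboratory values and their changes from baseline by visit, separately for the double-blind and single-blind periods, but only for values "collected up to the day of last dose of study treatment +28 days". SAP 5.8.6 sets the same limit for vital signs, at each "post-baseline visit (collected up to the day of last dose of study treatment +28 days".

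Other rules select values differently. SAP 5.8 says that in summary tables "only protocol scheduled measurements (as defined by e-CRF visit label) will be included". Protocol 10.6 shows assessments made outside their windows under the visit recorded on the CRF. Protocol 10.4.5.2 plans change from baseline to every scheduled assessment. SAP 1.2.4, which lists departures from the protocol's statistical section, does not mention a 28-day limit on safety summaries; it mentions 28 days only for exposure duration.

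On timing, protocol 5.1 gives evinacumab or "matching placebo every 4 weeks (± 4 days) on days 1, 29, and 57" in the double-blind period, and evinacumab "on days 85, 113, and 141" in the single-blind period. The schedule in SAP 10.4 puts week 12 on day 85 ± 4 and week 24 on day 169 ± 5, with hematology, chemistry and vital signs at both. Its footnotes add that "Patients will undergo end of double-blind treatment period assessments at the week 12 visit", and that at dosing visits "all blood samples should be collected before the dose of study drug is administered".

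The analysis of potentially clinically significant values (PCSV) uses a different window. It looks for any post-baseline "measurement that meets the PCSV criteria within the respective TEAE periods".

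**The concern.** A day limit that coincides with the nominal day of the visit it should capture leaves no room for the visit window. A patient can comply fully with the schedule and still have the end-of-period value left out of the by-visit table.

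The affected columns matter. Week 12 is the last visit at which the randomised groups can be compared before everyone receives evinacumab, and week 24 closes the treatment period. The trial enrolls at most about 50 patients and plans no inferential safety testing, so these descriptive tables are a main view of laboratory and vital-sign trends. A column whose n depends on the gap between infusion and visit is harder to interpret. A programmer would also face two rules, day limit and visit label, with no statement of which governs.

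**Working it through.** **Inputs.** Last double-blind infusion day 57 ± 4; week 12 visit day 85 ± 4; last single-blind infusion day 141 ± 4; week 24 visit day 169 ± 5 (protocol 5.1; SAP 10.4). Limit: last dose + 28 days (SAP 5.8.5, 5.8.6).

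**1. Nominal days.** 57 + 28 = 85 and 141 + 28 = 169. The limit equals the visit day in both periods.

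**2. Gap in general.** Let *a* be the infusion's offset from its nominal day and *b* the visit's offset. Gap = 28 + (*b* − *a*), so the value is excluded whenever *b* > *a*.
- Infusion on its nominal day: visits on days 86–89 (week 12) or 170–174 (week 24) are on-window but excluded.
- Visit on its nominal day: an infusion on days 53–56 or 137–140 also excludes it.
- Infusion and visit both one day late: the gap is 28 and the value is kept. What counts is the gap from the actual last infusion, not lateness in itself.

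**3. Largest on-window gap.** Week 12: 89 − 53 = 36 days. Week 24: 174 − 137 = 37 days.

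**4. Share of on-window combinations excluded.**
- Week 12: 9 × 9 = 81 pairs, 9 with *a* = *b*; (81 − 9)/2 = 36 have *b* > *a*; 36/81 = 44%.
- Week 24: 9 × 11 = 99 pairs, 9 with *a* = *b*; (99 − 9)/2 = 45 have *b* > *a*; 45/99 = 45%.

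**5. Dependence on timing.** The documents give no distribution of visit days, so these shares are assumptions.

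| Timing assumption | Week 12 | Week 24 |
|---|---|---|
| Independent, uniform within windows | 44% | 45% |
| Independent, triangular within windows | 43% | 44% |
| Independent, uniform within ± 1 day | 33% | 33% |
| Visit exactly 28 days after the actual infusion (*b* = *a*) | 0% | 0% |

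**6. Final infusion skipped, visits kept.** For week 24 the limit becomes 113 + 28 = day 141, and the nominal visit is 169 − 113 = 56 days after the last infusion. Even with the infusion at its latest (day 117) and the visit at its earliest (day 164), the gap is 47 days, so the value is excluded.

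**7. What still shows the values.** SAP 5.8 puts all measurements in listings. For PCSV and the ALT-versus-bilirubin plot (eDISH), the single-blind window runs to last dose + 168 days (SAP 4.8.1), so a late week 24 value stays in. At week 12, for patients who continue, the double-blind window ends the day before the first single-blind infusion. By date, a pre-dose sample taken on that infusion day falls outside the double-blind PCSV and eDISH analyses. That makes the week 12 column of the by-visit table more important.

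**The case against.** The strongest defence is that the parenthesis only chooses table columns: it keeps visits through week 12 or week 24 and leaves out the off-drug visits at weeks 28, 36 and 44. The exact nominal match fits that intention, as do the visit-label rules. This reading is possible, but strained, because the text limits when values are collected rather than which visits are shown. If it is what was meant, the sections should say so.

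Second, the week 12 half depends on how last dose is read. Elsewhere the SAP usually names the double-blind or single-blind dose when it means one (for example SAP 4.6 and 4.8.1). If it means the last dose overall here, patients who enter the single-blind period keep week 12. The opening reference in both sections to the respective treatment period favours the per-period reading but does not settle it. Week 24 is affected on either reading.

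Third, a reader might infer that patients who stop treatment because of adverse events are systematically removed. The documents do not support that. Permanent discontinuers are asked back for an early termination visit with week 12 or week 24 assessments (protocol 7.4.2), within 5 days in the double-blind period, and those values may fall inside the limit. Certain exclusion applies to patients who skip the final infusion but stay on schedule. Leaving a value taken some 56 days after dosing out of an on-treatment table can be defended, but it should be an explicit choice.

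Fourth, exclusion may be rare in practice. Dosing is every 4 weeks, and booking visits from the last infusion would make the offsets move together. That stands: the frequency cannot be determined from the documents.

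**Conclusion.** The point holds as a drafting defect. Read literally, SAP 5.8.5 and 5.8.6 drop protocol-compliant week 24 values, and on the per-period reading week 12 values, whenever the visit is more than 28 days after the actual last infusion. That conflicts with SAP 5.8 and protocol 10.6.

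The size is unknown. The 44% to 45% rests on independent, uniform timing within the windows, and the share falls toward zero if visits follow the actual infusion by 28 days. A reader might multiply the larger share by 50 patients to obtain a count of lost values; with no timing data and no allowance for dropout, the documents do not support such a count.

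Nor do they support saying that end-of-period safety data are lost. The effect is confined to descriptive by-visit laboratory and vital-sign tables. Listings keep everything, and late week 24 values remain in the PCSV and eDISH analyses. Severity is minor to moderate.

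**What to change.** In SAP 5.8.5 and 5.8.6, replace the day limit with assignment of scheduled values by e-CRF visit label. Let the pre-dose week 12 visit close the double-blind table and week 24 close the single-blind table.

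If a day limit is preferred, set it to at least last dose + 37 days, which drops 0 of the 81 and 0 of the 99 on-window combinations. This would still exclude patients who skip the final infusion (gap of at least 47 days at week 24), so the SAP should say whether that is intended.

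Under either option, state that last dose means the last dose of the period being summarised. Columns for the off-drug follow-up visits are optional.

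The cost is a wording change in two SAP sections, best made before the SAP is finalised. It needs no new data and no protocol amendment.

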9.4.3. Other Events that Require Accelerated Reporting to Sponsor

The following events also require reporting to the sponsor (or designee) within 24 hours of learning of the event:

Symptomatic Overdose of Study Drug: Accidental or intentional overdose of at least 2 times the intended dose of study drug within the intended therapeutic window, if associated with an AE.

Pregnancy: Although pregnancy is not considered an AE, it is the responsibility of the investigator to report to the sponsor (or designee), within 24 hours of identification, any pregnancy occurring in a female patient, or female partner of a male patient, during the study or within 24 weeks of the last dose of study drug. Any complication of pregnancy affecting a female study patient, or the female partner of a male study patient, and/or fetus and/or newborn that meets the SAE criteria

must be reported as an SAE. Outcome for all pregnancies should be reported to the sponsor.

Adverse Events of Special Interest: All AESI, serious and nonserious, must be reported within 24 hours of identification using the same reporting process as for SAE reporting, per Section 9.4.2. Adverse events of special interest for this study include the following:

- Anaphylactic reactions
- Allergic reactions and/or local injection site reactions that require consultation with another physician for further evaluation
- Increase in ALT or AST: $\geq 3 \times$ ULN (if baseline $<$ ULN), or ≥ 2 times the baseline value (if baseline \geq ULN)
- Pregnancy
- Symptomatic overdose with evinacumab
- Neurocognitive events
- New onset of diabetes: The definition of new onset of diabetes will be the following:
 - Type 1 or type 2 diabetes TEAE (grouping of Medical Dictionary for Regulatory Activities [MedDRA®] terms will be specified in the SAP)and/or
 - At least 2 values of HbA1c $\geq 6.5\%$ during the TEAE period. **NOTE:** For patients with only a single measurement available during the TEAE period, a single value $\geq 6.5\%$ will be considered and qualify the patient as new onset of diabetes by default. For patients with several HbA1c measurements but only with the last one $\geq 6.5\%$, this single value $\geq 6.5\%$ will be considered and qualify the patient as new onset of diabetes by default.and/or

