Patient listing of possible Hy's law cases identified by treatment group (i.e., patients with any elevated ALT >3 x ULN, and associated with an increase in bilirubin >2 x ULN, concomitantly or not) with ALT, AST, ALP, total bilirubin, and if available direct and indirect bilirubin will be provided.

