10.3. Criteria for Potentially Clinically Significant Values (PCSV)

Parameter	PCSV
Clinical chemistry	
ALT	By distribution analysis: >2 ULN and baseline ≤ 2 ULN >3 ULN and baseline ≤ 3 ULN >5 ULN and baseline ≤ 5 ULN >10 ULN and baseline ≤ 10 ULN >20 ULN and baseline ≤ 20 ULN
AST	By distribution analysis: >2 ULN and baseline ≤ 2 ULN >3 ULN and baseline ≤ 3 ULN >5 ULN and baseline ≤ 5 ULN >10 ULN and baseline ≤ 10 ULN >20 ULN and baseline ≤ 20 ULN
Alkaline Phosphatase	> 1.5 ULN and baseline ≤ 1.5 ULN
Total Bilirubin	> 1.5 ULN and baseline ≤ 1.5 ULN > 2 ULN and baseline ≤ 2 ULN
Conjugated bilirubin	> 35% total bilirubin (when total bilirubin >1.5 ULN)
ALT and Total Bilirubin	ALT > 3 ULN and Total Bilirubin > 2 ULN and baseline ALT≤3 ULN or Total bilirubin ≤ 2 ULN
CPK	> 3 ULN and ≤ 5 ULN and baseline ≤ 3ULN >5 ULN and ≤ 10 ULN and baseline ≤ 5 ULN >10 ULN and baseline ≤ 10 ULN
Creatinine	≥ 150 µmol/L (adults) ≥ 30% from baseline ≥ 100% from baseline
CrCl (mL/min) (Estimated creatinine clearance based on the Cokcroft-Gault equation)	≥15 - <30 (severe decrease in GFR) ≥30 - < 60 (moderate decrease in GFR) ≥60 - <90 (mild decrease in GFR) ≥ 90 (normal GFR)
eGFR (mL/min/1.73m ²) (Estimate of GFR based on an MDRD equation)	≥15 - <30 (severe decrease in GFR) ≥30 - < 60 (moderate decrease in GFR) ≥60 - <90 (mild decrease in GFR) ≥ 90 (normal GFR)

Parameter	PCSV
Uric Acid	
Hyperuricemia:	>408 µmol/L
Hypouricemia:	<120 µmol/L
Blood Urea Nitrogen	≥17 mmol/L
Chloride	<80 mmol/L ≥115 mmol/L
Sodium	≤129 mmol/L ≥ 160 mmol/L
Potassium	< 3 mmol/L ≥ 5.5 mmol/L
Glucose	
Hypoglycaemia	≤ 3.9 mmol/L and < LLN
Hyperglycaemia	≥ 7 mmol/L (fasted); ≥ 11.1 mmol/L (unfasted)
HbA1c	>8%
Albumin	≤25 g/L
CRP	> 2 ULN or ≥10 mg/L, if ULN not provided
Hematology	
WBC	< 3.0 Giga/L (3000/ mm ³) (Non-Black) < 2.0 Giga/L (2000/ mm ³) (Black) ≥16.0 Giga/L (16000/ mm ³)
Lymphocytes	>4.0 Giga/L
Neutrophils	< 1.5 Giga/L (1500/ mm ³) (Non-Black) < 1.0 Giga/L (1000/ mm ³) (Black)
Monocytes	>0.7 Giga/L
Eosinophils	> 0.5 Giga/L (500/ mm ³) or > ULN if ULN ≥ 0.5 Giga/L
Hemoglobin	≤115 g/L (Male); ≤95 g/L (Female) ≥185 g/L (Male); ≥165 g/L (Female) Decrease from Baseline ≥15 g/L Decrease from Baseline ≥20 g/L
Hematocrit	≤0.37 v/v (Male) ; ≤0.32 v/v (Female) ≥0.55 v/v (Male) ; ≥0.5 v/v (Female)
RBC	≥6 Tera/L

Parameter	PCSV
Platelets	< 100 Giga/L (100 000/mm ³) ≥700 Giga/L (700000/mm ³)
Urinalysis	
pH	≤4.6 ≥8
Vital signs	

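### The SAP's joint liver screen pairs bilirubin with ALT only, so a patient with AST above 3 x ULN, ALT at or below 3 x ULN and bilirubin above 2 x ULN is not flagged as a possible Hy's law case

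*SAP*

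**What the plan says.** Three SAP outputs join a transaminase to bilirubin.

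- **Possible Hy's law listing (SAP 5.8.5).** It selects "patients with any elevated ALT >3 x ULN, and associated with an increase in bilirubin >2 x ULN, concomitantly or not". The listing is then to be printed "with ALT, AST, ALP, total bilirubin, and if available direct and indirect bilirubin will be provided". AST is thus a displayed column and not a selection criterion.
- **eDISH plot (SAP 5.8.5).** This is a "graph of distribution of peak values of ALT versus peak values of total bilirubin", divided into quadrants by a "vertical line corresponding to 3 x ULN for ALT and a horizontal line corresponding to 2 x ULN for total bilirubin".
- **Combined PCSV row (SAP 10.3).** The criterion is "ALT > 3 ULN and Total Bilirubin > 2 ULN and baseline ALT≤3 ULN or Total bilirubin ≤ 2 ULN". There is no matching row for AST with bilirubin.

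Elsewhere the two enzymes are handled alike. Protocol 6.2.2, exclusion 19, applies one threshold to AST or ALT. Protocol 9.4.3 defines the hepatic event of special interest as "Increase in ALT or AST", with the same multiples for both. In SAP 10.3 the single-enzyme PCSV rows for ALT and AST carry identical cut-offs (2, 3, 5, 10 and 20 x ULN).

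**The concern.** A Hy's law listing and an eDISH plot exist so that a reader does not have to match liver enzymes to bilirubin by hand. If both depend on ALT, a case in which AST carries the transaminase signal is left out. The report could then state that no possible Hy's law case was identified when such a patient was in the data. The SAP's listing is otherwise built to be sensitive, since it does not require the two elevations to coincide in time. Relaxing the timing while leaving out one of the two transaminases sits uneasily with that purpose.

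**Working it through.** The plan states no figure to reproduce, and no sample size or error rate bears on the point. The check is to apply each rule to one assumed patient. The values are illustrative and not from the documents: normal baseline, peak AST 6 x ULN, peak ALT 2.5 x ULN, peak total bilirubin 2.5 x ULN.

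| Rule | Test | Result |
|---|---|---|
| Hy's law listing, SAP 5.8.5 | ALT 2.5 > 3? | No: not listed, so the AST column is never shown |
| Combined PCSV row, SAP 10.3 | ALT 2.5 > 3? | No: not counted |
| eDISH, SAP 5.8.5 | point (ALT 2.5, bilirubin 2.5) against lines at 3 and 2 | Upper-left quadrant; AST not visible |
| AST PCSV rows, SAP 10.3 | 6 > 2, > 3, > 5 | Met at all three |
| Bilirubin PCSV rows, SAP 10.3 | 2.5 > 1.5, > 2 | Met at both |
| ALT PCSV row, SAP 10.3 | 2.5 > 2 | Met |
| Protocol 9.4.3 event | AST 6 ≥ 3, baseline below ULN | Met |

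Two variations show where the gap begins and ends.

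- **Raise ALT to 4 x ULN, all else equal.** Since 4 > 3 and 2.5 > 2, the patient is listed with AST displayed, counted in the combined row and plotted in the upper-right quadrant. The gap therefore exists only while ALT is at or below 3 x ULN.
- **Keep ALT at 2.5 and change the rule to ALT or AST.** The larger multiple is max(2.5, 6) = 6 > 3, with bilirubin 2.5 > 2. The patient enters the listing and the combined row, and the eDISH point moves to (6, 2.5), in the upper-right quadrant. Every patient selected under the ALT-only rule is still selected.

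Two further places in the SAP were checked for something that would supply the joint flag.

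- The list of events of special interest in SAP 4.8.1.2 and Appendix 10.2 has eight items, none of them an ALT or AST increase. The protocol's AST event therefore has no matching output there.
- At the cohort 1 interim analysis, SAP Section 7 restricts general laboratory output to PCSV summary tables. The ALT-only combined row is then the only laboratory rule joining a transaminase to bilirubin.

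**The case against.** The strongest reply is that nothing is hidden. The AST and bilirubin elevations each have their own PCSV rows, and SAP 5.8.5 provides patient-level listings of values meeting PCSV criteria. With about 50 patients, a careful reader could match them. Protocol 9.4.3 requires an AST rise to be reported to the sponsor within 24 hours with no bilirubin condition. Protocol 8.2.5.4 requires significantly abnormal results to be repeated. SAP 5.8.1 tabulates hepatic disorder events from a broad standard query, and the data monitoring committee reviews safety. All of this stands, and it limits the point to a missing joint flag. It does not remove the point. Cross-matching by hand is the work the listing is meant to do, the hepatic query depends on reported event terms, and the reporting rule is not an analysis output.

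Three stronger readings are tempting but unsupported.

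- A reader might infer that any patient with high AST and high bilirubin appears in no combined liver output. That is wrong twice: with ALT also above 3 x ULN the patient is captured everywhere, and with lower ALT the patient is still plotted on eDISH, because the SAP states no selection step for that graph.
- A reader might infer that the SAP contradicts the protocol. The protocol's event is a single-enzyme reporting rule and Hy's law screening is an enzyme-plus-bilirubin rule. Neither document says the joint screen must use AST. This is a gap in coverage.
- A reader might try to size the loss from the trial's sample size or from the alcohol intake allowed in Protocol 6.2.1. A zero-event bound would apply to any event and would not measure what ALT-only selection misses. The documents give no enzyme pattern by alcohol intake, and Protocol 6.2.2 excludes alcohol abuse, including binge drinking, within a year of screening.

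**Conclusion.** The concern holds in a limited form. A patient with AST above 3 x ULN, ALT at or below 3 x ULN and total bilirubin above 2 x ULN is not identified as a possible Hy's law case by the listing, the combined PCSV row or the eDISH upper-right quadrant. That patient's values remain visible in separate outputs. The size in patients cannot be derived from the documents, and it may be zero. The conclusion rests on two readings: that eDISH plots all patients with post-baseline values, and that the baseline clause of the combined row means baseline ALT within its limit or baseline bilirubin within its limit. The first decides only whether the patient is still plotted; the second does not affect the gap, because the row already fails on ALT. This is a worthwhile and inexpensive improvement to a descriptive safety screen. It does not affect the efficacy analysis.

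**What to change.** - **SAP 5.8.5, listing:** select on ALT or AST above 3 x ULN together with total bilirubin above 2 x ULN, keeping the existing rule that the two need not coincide.
- **SAP 10.3, combined row:** make the same change and apply the matching baseline condition to whichever enzyme qualifies. That is, AST above 3 x ULN counts if baseline AST was at or below 3 x ULN or baseline bilirubin was at or below 2 x ULN.
- **SAP 5.8.5, eDISH:** put the larger of peak ALT/ULN and peak AST/ULN on the horizontal axis, or add a second panel for AST.
- **Listing columns:** add CPK, so that AST of muscle origin can be recognised.

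The cost is a few lines of SAP text and a small programming change. AST, total bilirubin and CPK are already in the chemistry panel in Protocol 8.2.5.4, so no new sample or visit is needed. The downside is that some muscle-origin AST rises will be listed and need a comment.
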